IRB Study Number: TBD

Title: Patient Well-Being Research Project 01-23-17 to IRB

Protocol Title

Title: **Patient Well-Being Research Project**

Objectives

Well-being is a positive state affairs in six domains of life: interpersonal, community, occupational, physical, psychological, and economic (I COPPE). The purpose of the study is to evaluate the effectiveness, feasibility, and acceptability of an online intervention designed to promote skills and self-efficacy in the I COPPE domains of life.

Overview

The study design is a prospective, double-blind, longitudinal randomized controlled trial (RCT). The control group will be wait-listed. Well-being and self-efficacy measures will be administered at baseline (T1), 30 days-post baseline (T2) and 60 days -post baseline (T3). Approximately 6,000 University of Miami Health System (UHealth) patients who visit the UM Lennar Foundation Medical Center may have the opportunity to be invited to participate in the study. A maximum of 500 patients will be enrolled. Recruitment will take place on-site through IRB approved study flyers at the UM Lennar Foundation Medical Center. Eligibility verification, data collection, randomization, intervention group activities, and incentive distribution will take place entirely online. A secure website will be the sole location where all research activities will take place. Participants will only be able to access the site using unique user names and passwords. After consenting, participants in the intervention group will participate in online activities within 30 calendar days. Participants in the wait-list control group will be given access to the intervention after all study participants have completed the three survey battery administrations. The study team has full support at the highest administrative levels of the University of Miami.

IRB Study Number: TBD

Title: Patient Well-Being Research Project 01-23-17 to IRB

Intervention condition: Through the online program named Fun For Wellness (FFW), participants will: 1) watch original videos with vignettes performed by professional actors; 2) read and/or watch mini-lectures that teach skills for behavior change; 3) engage in self-reflection exercises, 4) play original interactive games related to vignettes and mini-lectures; 5) interact with other FFW users via chat room functions and; 6) watch funny narrated video clips about well-being.

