As previously mentioned, the study design is a prospective, double-blind, longitudinal randomized controlled trial (RCT). Well-being and self-efficacy measures will be administered at baseline (T1), 30 days-post baseline (T2) and 60 days -post baseline (T3). Approximately 1,000 University of Miami Health System (UHealth) patients from the UM Lennar Medical Center will be invited to participate in the study. A maximum of 500 patients will be enrolled. Recruitment will take place on-site through distribution of IRB approved study flyers at the UM Lennar Center. Eligibility verification, data collection, randomization, intervention/control group activities, and incentive distribution will take place entirely online. A secure website will be the sole location where all research activities will take place.

Data Collection Plan

At each individually scheduled data collection point, participants will have a 7-day window to return to the website and provide their survey data (see Battery below) in order to receive an incentive. If they do not return within the 7-day timeframe to provide survey data, this will be considered missing data. All participants must complete/participate in each survey battery set to be credited money in the study’s Amazon electronic gift card account. Completion of each

IRB Study Number: TBD

Title: Patient Well-Being Research Project 01-23-17 to IRB

survey will be marked by a final SUBMIT button for the participant to click on when they are ready to submit each survey as completed. During each data collection time (i.e., T1, T2, T3), each participant will be able to see how far he/she has progressed toward completion of a survey battery set in order to be eligible for the assigned incentive value for that particular data collection time (i.e. \$5, \$10, \$15). This will be accomplished by providing each participant with a progress bar that will be visually represented on the participant's data collection page. The participant will be able to view how many surveys and items he/she has to complete to achieve completion.

Remuneration Plan

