Participants will be recruited by being offered a research study invitation flyer, in-person. They will receive the flyer when checking in for their pre-registered medical appointment at the University of Miami's UHealth Lennar Foundation Medical Center. Upon check-in, a clinical access representative will ask each patient if they are interested in receiving an invitation flyer for a research study.

Participant recruitment. The IRB approved study recruitment flyers will begin to be offered to patients at the UM Lennar Medical Center on day 1 of the 24-day recruitment window. See figure 1 below for a visual overview of the real-time recruitment window procedures and communication components:

Figure 1

Recruitment Window

2) Patient Well-Being Research Project personal account request. Each recruited person who wishes to, will have the opportunity to visit the Patient Well-Being Research Project log-in page. To ensure the probability the project is limiting entry to only UM Lennar Medical Center patients who were handed an invitation flyer while on-site at the medical center, each visitor to the log-in page will be immediately prompted to enter a valid code that was printed on the

IRB Study Number: TBD

Title: Patient Well-Being Research Project 01-23-17 to IRB

invitation flyer they were given, in addition to their email address. They will then create a unique username and their own password for their research project account which will be stored in the research project database. All e-mail addresses will be encrypted on the research team's end so the researchers will be blind to the identity of the recruited subjects.

3) E-mail verification procedure and account activation. After respondents have created a personal account, they will receive an automated e-mail delivered to the e-mail address they provided when they created their personal account. They will be prompted to check their e-mail and click on the verification hyperlink to verify their e-mail address and activate the account they created. The salutation field of the automated e-mail verification will be populated with the username the respondent typed in when they requested an account. As soon as they click on the e-mail verification hyperlink, their account will become activated.

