Title: Patient Well-Being Research Project 01-23-17 to IRB

represented visually on the user's page as they complete each assessment to show their level of battery completion. Below is the T1 battery set of assessments that all consented participants will be administered prior to being randomized to a condition group.

1. FFW Demographics Questionnaire (9 items)
2. Self-Efficacy to Comply Measure (1 item)
3. I COPPE Scale- 30-day version (21 items)
4. SEWB Scale- 30-day version (21 items)
5. I COPPE Actions Scale- Revised (19 items, including 1 attention filter item)
6. Chronic Conditions Checklist (20 items)
7. SF-36 v2 (36 items)

On day 14 of the recruitment window, a baseline (T1) data collection battery set reminder e-mail will be sent to all consented participants who have not completed T1 data collection letting them know they have 10 more days to complete the T1 battery set of surveys. Here is the e-mail subject line: ***Patient Well-Being Research Project: Reminder to complete Survey Set #1.***

7) Participant incentive #1 credit deposit. After each participant submits the final survey, a visual and sound action will show the \$5 Amazon electronic gift card credit into the participants' Patient Well-Being Research Project bank account.

8) Participant randomization and condition group assignment. Participants who have completed the full T1 battery will be randomly assigned in real time to either the intervention condition or the wait-list control condition. Randomization and assignment will be done solely by the computer program so researchers will be blind to participant randomization and group assignment. The computer program will use a 2:1 randomization algorithm so that there are twice as many intervention participants as control participants. Participants will be randomly assigned based on their sequential order in the assignment line up which will be established at the exact time of each participant's submission of the battery of the first set of surveys (i.e. T1).

IRB Study Number: TBD

Title: Patient Well-Being Research Project 01-23-17 to IRB

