The first participant who submits their T1 battery will be assigned control or intervention based on a digital coin flip. For each additional participant who submits their T1 battery, if we need another person to fulfill the intervention (2:1) ratio, that person will be assigned to the intervention condition. The same with control, if more control participants need to be assigned to that condition, then the participant will be added to the control group. If we already have an exact 2:1 ratio, the participant will be assigned to one of the two conditions based on a digital coin flip.

9) Participant condition group access. As soon as participants complete the T1 battery set of surveys and are randomized by the computer, they will be sent a welcome e-mail. Here is the e-mail subject line: *Welcome to the Patient Well-Being Research Project*.

Intervention participants will have immediate access to the Fun For Wellness and control participants will be wait-listed. Participants in the intervention group may access the Patient Well-Being Research Project site during all hours of the 30-day access window. Control group participants will be informed they have been randomly assigned to the wait-list condition and will be given eventual 30 days of access to the online well-being program at the end of the 60-day study.

After 30 days, participants in the intervention group will no longer have access to the online program at the Patient Well-Being Research Project site. Participants from both condition groups may still log in to see how much credit they have in their account to redeem Amazon electronic gift card codes. Participants in both groups will be sent reminder e-mails to complete the survey set for the second time (T2: 30-days post baseline). After 30 more days have passed (T3: 60-days post baseline), participants will receive reminder e-mails to complete the survey set for the third time.

IRB Study Number: TBD

Title: Patient Well-Being Research Project 01-23-17 to IRB

10) Participant e-mail reminder plan. Two types of e-mail reminders will be automatically sent to participants during the 60-day study period. The first type of e-mail will encourage continued participation in the online program. The second type of email will encourage completion of the surveys.

a) Email to encourage continued participation:

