We will send one participation e-mail during the intervention participant's 30-day access period. One e-mail will be sent to each participant on day 4 of their 30-day access period.

Here is the day 4 participation encouragement e-mail subject line: ***Patient Well-Being Research Project- 26 more days to keep visiting us during your access time 😊***

b) Email to encourage survey completion:

We will send four of these survey completion emails to participants in both condition groups. For each data collection time (T2; T3), we will send two survey battery reminder e-mails. At T2, immediately after the intervention group participant's 30-day access period, and after 30 days have passed since the T1 baseline for the wait-list control participant (i.e., day 31), we will send one survey battery reminder e-mail. Four days later, we will send another survey battery reminder e-mail to those participants who have still not completed T2 data collection.

Here is the T2 (day 31) initial survey battery reminder e-mail subject line: ***Patient Well-Being Research Project: Reminder 7 days to complete Survey Set #2.***

IRB Study Number: TBD

Title: Patient Well-Being Research Project 01-23-17 to IRB

Here is the T2 (day 34/day 4 of 7-day window) initial survey battery reminder e-mail subject line: ***Patient Well-Being Research Project: Reminder 3 days to complete Survey Set #2.***

On the first day of T3, which corresponds to 60-days post baseline, we will send one survey battery reminder e-mail that the 7-day window is open for participants to complete the third survey battery set. Four days later, we will send another survey battery reminder e-mail to those participants who have still not completed T3 data collection.

Here is the T3 (60-day post baseline) initial survey battery reminder e-mail subject line: ***Patient Well-Being Research Project: Reminder 7 days to complete Survey Set #3.***

Here is the T3 (60-day post baseline) (day 64/day 4 of 7-day window) initial survey battery reminder e-mail subject line: ***Patient Well-Being Research Project: Reminder 3 days to complete Survey Set #3.***

Battery Set of Surveys Content

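### The trial is labelled double-blind, but participants in both arms know their allocation when they rate their own outcomes at T2 and T3

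*Combined protocol and SAP*

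**What the plan says.** The Overview gives the design as "The study design is a prospective, double-blind, longitudinal randomized controlled trial (RCT"), and Study Procedures repeats it: "the study design is a prospective, double-blind, longitudinal randomized controlled trial (RCT").

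Under Study Procedures, item 9 (Participant condition group access), the arms are handled openly once the T1 battery is complete and the computer has randomized: "Intervention participants will have immediate access to the Fun For Wellness and control participants will be wait-listed". For the comparator, "Control group participants will be informed they have been randomly assigned to the wait-list condition", with access promised after the 60-day study. Item 10 (Participant e-mail reminder plan) sends intervention participants a day-4 message whose subject line includes "26 more days to keep visiting us during your access time".

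The word blind is used in two other places. Item 8 (Participant randomization and condition group assignment) has the computer alone randomize and assign, "so researchers will be blind to participant randomization and group assignment". Item 2 (personal account request) encrypts e-mail addresses, "so the researchers will be blind to the identity of the recruited subjects".

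On timing, item 7 describes the T1 battery as one that "all consented participants will be administered prior to being randomized to a condition group". T2 and T3 follow at 30 and 60 days after baseline.

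**The concern.** Double-blind normally tells a reader that participants, and at least one other party such as assessors or investigators, do not know the allocation. Here participants are also the outcome assessors, so their masking matters most for these endpoints, and the procedures rule it out.

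If the label passes into a report, readers would take the self-rated H1 to H3 results as protected against expectancy and reporting effects. They are not. The contrast is access to the program against a wait-list that participants know they are on, and by itself it cannot separate what the program does from what people expect or feel they should report. H3 is especially exposed: the mediator (self-efficacy) and the outcomes are both rated by people who know their arm, so a shared reporting effect could contribute to the product of the two pathways being tested. The documents do not state this limit.

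**Working it through.** The documents give no figure to reproduce. The check is a comparison of every statement on masking, disclosure and assessment.

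**Who knows the arm, and when**

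| Party | What the documents provide | Masked to arm? |
|---|---|---|
| Control participants | Told they are wait-listed (item 9); no substitute program (Overview, Wait-list control condition; Group Conditions, Wait-list control) | No, stated outright |
| Intervention participants | Immediate access (item 9); day-4 e-mail (item 10); a \$15 module credit only this arm can earn (Remuneration Plan); a 15-item Experience Survey at T2 for this arm only (Battery Administration Schedule) | No, follows from access |
| Outcome assessors | The participants themselves: I COPPE, SEWB and SF-36v2 are answered online by them (Description of Measures) | No |
| Researchers | Blind to computer randomization and assignment (item 8) | Yes at that step; nothing said about later |
| Analyst | No statement | Unknown |

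The blinding in item 2 concerns identity, and the coding described under Data storage methods & data security concerns confidentiality. Neither masks arm.

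**Timing.** T1 is completed before randomization. The notice to controls has no date of its own, but it sits in the same item as the welcome e-mail sent on randomization and promises access at the end of the 60-day study. It therefore precedes T2 (day 30) and T3 (day 60).

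**Extent.** Items feeding H1 to H3 at each time, from the Battery Administration Schedule:

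- I COPPE 21 + SEWB 21 + SF-36v2 36 = 78 items
- Three times: 3 × 78 = 234 item responses per participant with complete data
- After allocation is known: 2 × 78 = 156, and 156/234 = 66.7%

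This percentage is simply two of three assessments. It shows that every post-randomization response is unmasked; it does not measure bias. Everyone randomized is affected: at the maximum of 500, the 2:1 ratio gives 500 × 2/3 ≈ 333 and 500 × 1/3 ≈ 167.

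**Whether researcher masking could last.** Participation measures (number of challenges completed, time on modules, visits) come from use of the program, and Description of Measures plans comparisons of effect by dosage. Those logs and the intervention-only survey would reveal the arm to anyone who sees them.

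**Related slip.** In the Data Analysis Plan, the H1 power text describes the arm variable as treatment against a placebo. H1 itself names the wait-list, and the matching H2 text says only control. No placebo exists in this trial.

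**The case against.** The best defence concerns weight. The comparator is not hidden: in the Overview the wait-list is named in the sentence directly after the label, and H1 and H2 define the contrast against it. A reader of the whole protocol is not misled about what controls receive. The harm arises only if the label is carried forward, and correcting it removes no bias. Difficulty in separating expectancy from program effect is common to any open wait-list design with self-report, so it could be left to the report's limitations. The knowledge of the intervention arm and the date of the notice to controls are inferred, not stated.

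Parts of this stand. The 67% says nothing about bias. The placebo wording is a separate minor slip and adds no weight to the masking point. Any replacement wording must not claim more researcher masking than item 8 supports.

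The main point is unaffected. Disclosing the wait-list is what makes the label contradictory, and no other passage rescues it. Both inferences are sound: someone using the program knows they have it, and a promise of access after 60 days has to be made before then. Blinding is a core design attribute, stated twice, and the plan should not assert one that its own procedures exclude.

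**Conclusion.** The concern holds. The plan claims a design property it does not have. Participants in both arms, who are also the assessors of all H1 and H2 outcomes and of the H3 mediator, know their allocation at T2 and T3. At most one party, the researchers, is masked, and the text supports this only for randomization and assignment.

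All randomized participants and both follow-up assessments are affected. The size of any reporting bias cannot be derived from the documents, and none is estimated. The conclusion rests on two readings: that access to the program reveals the arm to those who receive it, and that the notice to controls accompanies the post-randomization welcome e-mail. This should be corrected because it changes what the self-rated results may be said to show. It is no obstacle to running the trial.

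**What to change.** 1. In the Overview and in Study Procedures, remove the double-blind label and say instead: *participants not blinded; randomization and assignment done by computer, with researchers blind to that step.*
2. Have the sponsor state who else, if anyone, is masked to arm and until when, given that the participation logs and the intervention-only Experience Survey reveal it. Until that is answered, the design statement should claim no further masking.
3. Add one sentence to the Data Analysis Plan: *H1 to H3 conclusions concern access to FFW versus a known wait-list and cannot separate program effect from expectancy or reporting effects in self-rated outcomes.*
4. In the H1 power text, change the placebo wording to wait-list control.

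The cost is wording in three places, one statement on masking and one sentence on scope. Sample size, procedures, data collection and models are unchanged. The stated design becomes less favourable but matches what will be done.

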Wait-list control condition: Participants will conduct their lives as usual during the 30-day intervention period.

Screening and Enrollment

Study Participants:

All participants will be 18 years old and above, patients at the UHealth Lennar Foundation Medical Center, and will have no prior or current exposure to the FFW intervention.

The maximum number of subjects we intend to screen is 1,000.

The total number of subjects we intend to enroll is 500.

Exclusion/Inclusion Criteria

The study population will be patients at the UHealth Lennar Foundation Medical Center. The criteria for exclusion of participants are:

- 1) Those under the age of 18
- 2) Those not patients at the UHealth Lennar Foundation Medical Center
- 3) Those who have ever participated in the FFW intervention in another study

Rationale for exclusions: 1) Individuals who are not patients at the UHealth Lennar Foundation Medical Center will be excluded because we would like to generalize findings to patients at the UHealth Lennar Foundation Medical Center.

IRB Study Number: TBD

Title: Patient Well-Being Research Project 01-23-17 to IRB

2) Individuals under the age of 18 will be excluded as the program content and self-assessment tool have been created for an adult population.

3) Individuals who are/have been exposed to the FFW intervention will be excluded to avoid threats to the study's internal validity.

The criteria for inclusion of participants are:

- 1) Adults aged 18 and above
- 2) Those who are patients at the UHealth Lennar Foundation Medical Center.
- 3) Those who have never participated in the FFW intervention in another study.

Background

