4) Screening. As soon as the verified account holder logs-into the Patient Well-Being Research Project, the respondent will be presented with 3 screening questions to assess inclusion/exclusion criteria. The respondent needs to answer both questions affirmatively to be qualified to move on and read the consent form. Respondents who do not affirm the first two screening questions and/or affirm the third, will be terminated from the study and locked out of further access to the research project website. Below are the screening questions and the messages excluded respondents will receive:

a) Respondent is first asked:

i) Are you at least 18 years old?

yes = will continue to second inclusion/exclusion criterion question

no = will be excluded and blocked from further access to the website and presented with the following message:

“Thank you for your help. At this time it appears you do not meet criteria for the current study. However, future studies and software development

testing will be occurring. Please visit us again at the next opportunity. We sincerely appreciate your time and effort. ”

b) Continuing respondents are asked:

ii) Are you currently a patient at the University of Miami Lennar Foundation Medical Center?

yes = will continue to Consent page

no = will be excluded and blocked from further access to the website and presented with the following message:

“Thank you for your help. At this time it appears you do not meet criteria for the current study. However, future studies and software development testing will be occurring. Please visit us again at the next opportunity. We sincerely appreciate your time and effort. ”

c) Continuing respondents are asked:

iii) Are you now, or have you ever participated in activities of the Fun For Wellness online program?

yes = will be excluded and blocked from further access to the website and presented with the following message:

“Thank you for your help. At this time it appears you do not meet criteria for the current study. However, future studies and software development testing will be occurring. Please visit us again at the next opportunity. We sincerely appreciate your time and effort. ”

no = will continue to Consent page

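### The online screening text contradicts itself: the question ii 'yes' branch goes to consent, bypassing the prior-exposure question that the rest of the plan requires first

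*Combined protocol and SAP*

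**What the plan says.** Step 4) Screening, under Recruitment Window Procedures, opens by stating that "the respondent will be presented with 3 screening questions to assess inclusion/exclusion criteria". It continues: "The respondent needs to answer both questions affirmatively to be qualified to move on and read the consent form". The termination rule follows: "Respondents who do not affirm the first two screening questions and/or affirm the third, will be terminated from the study".

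The questions are then listed with a destination for each answer. Question i (age) has the branch "yes = will continue to second inclusion/exclusion criterion question". Question ii (current patient at the centre) has the branch "yes = will continue to Consent page". Question iii asks "Are you now, or have you ever participated in activities of the Fun For Wellness online program"; a yes excludes and a no leads to consent. Questions ii and iii carry the same short lead-in, addressed to respondents who are continuing.

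Elsewhere, Study Participants says that participants "will have no prior or current exposure to the FFW intervention". The third exclusion criterion bars people who have taken part in FFW in another study, with the rationale that "Individuals who are/have been exposed to the FFW intervention will be excluded to avoid threats" to internal validity. The text closing the screening step says that only respondents who meet the inclusion criteria are sent on to the consent screens.

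**The concern.** The question i branch names the next question. The question ii branch should do the same but names the consent page. Lines that assign a destination to each answer are the part of a protocol that a web programmer or tester is most likely to follow literally, and here that would let a respondent consent without being asked about earlier FFW use.

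The exclusion at stake is one that the plan itself ties to internal validity. People who already know the programme could enter either arm, so the wait-list group would no longer be reliably unexposed at baseline. Such people exist: Justification of Online Intervention reports an earlier randomized trial of FFW in an employee sample.

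**Working it through.** The plan states no figure to reproduce. The check is to trace the branch lines and compare them with the rule in the opening paragraph of the same step.

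**Branch lines in step 4) Screening**

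| Question | Answer | Destination as written |
|---|---|---|
| i, age 18 or over | yes | question ii |
| i | no | excluded |
| ii, current patient | yes | consent page |
| ii | no | excluded |
| iii, FFW participation | yes | excluded |
| iii | no | consent page |

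Totals: 1 to question ii, 3 to exclusion, 2 to consent, 0 to question iii; 1 + 3 + 2 + 0 = 6.

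**Answer patterns.** Three yes/no questions give 2 × 2 × 2 = 8 patterns.

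- Branch lines read alone: consent needs yes to i and yes to ii, and the answer to iii has no influence. That admits 1 × 1 × 2 = 2 patterns, yes/yes/no and yes/yes/yes.
- Termination rule: consent needs yes to i, yes to ii and no to iii. That admits 1 × 1 × 1 = 1 pattern, yes/yes/no.
- Difference: 2 − 1 = 1 pattern, yes/yes/yes, an adult patient with prior or current FFW participation.

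**Paths through the screen**

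- Branch lines read alone give 3: no (excluded), yes-no (excluded), yes-yes (consent).
- With question ii 'yes' leading to question iii there are 4: no, yes-no and yes-yes-yes (all excluded), and yes-yes-no (consent). Only this version agrees with the termination rule and the eligibility criteria.

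**Is there another check on prior exposure in the visible text?**

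- The Overview places eligibility verification entirely online.
- The flyer code at account creation is meant to limit entry to patients who were handed a flyer. It does not test FFW use.
- E-mail addresses are encrypted so that researchers do not know who the recruits are, and the computer alone randomizes. No staff review of eligibility is described.
- The baseline battery lists no prior-FFW measure, and the demographic variables named under Description of Measures do not include one.

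Question iii is therefore the only described step that applies this exclusion, and nothing described would identify an exposed participant afterwards.

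**The case against.** The strongest reply is that nobody reading the whole section would skip question iii. Its lead-in addresses continuing respondents; since those who answer no to question ii are blocked, it can only mean those who answered yes. The section also announces three questions, states what happens when the third is affirmed, and gives question iii its own exclusion message. On this view the line is a drafting slip and the exclusion is fully specified.

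Most of that stands. The intention is not in doubt, and the lead-in means that question iii is bypassed only if the branch lines are read without it. What remains is that two instructions in one step give different destinations for the same answer. The nearby sentence about answering both questions affirmatively does not settle the matter: it can mean questions i and ii as necessary conditions, which is consistent with the rule, but it also fits a two-question gate. For that reason it needs clarifying but is not counted as a second contradiction.

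A reader might go further and infer that question iii is never asked, that the exclusion is unenforced, or that exposed patients entered the trial. The documents support none of these. They do not show how the site was programmed, the recruitment-window figure and the consent pages are not available here, and the overlap between the earlier employee sample and this centre's patients is not stated.

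**Conclusion.** The point holds as a minor internal inconsistency: one of six branch lines conflicts with the opening rule, the lead-in to question iii, the third exclusion criterion and the closing text of the same step. It is not a questionable design choice, since nothing suggests that anyone meant to omit the question.

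The mismatch in the text is certain. The consequence is conditional on the site having been built from that line and on previously exposed people being among those screened. The documents give no number of such people, so neither the number affected nor any bias can be estimated. The counts of lines and paths describe the text only, not the size of an effect.

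**What to change.** 1. Under question ii, change the destination of a yes answer from the consent page to the third screening question, so that only a no at question iii leads to consent.
2. In the opening paragraph, replace the wording about both questions with an explicit rule: yes to questions i and ii and no to question iii.
3. Before launch, run the four answer paths on the live screen and confirm that only yes-yes-no reaches the consent page.

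The cost is one branch line, one clarifying phrase and a test of four paths. No new criterion is added; the change makes the text match the exclusion already adopted.
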